#### 3.5 Recruitment

Potential participants admitted to participating floors in the study will be identified in the EMR. Research coordinators will approach patients to participate in the study within 1-2 days of admission. The recruitment process will be documented and attested by the Investigators and their delegates.

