#### 4.3 Research Plan

- a. *Study Population:* In order to participate in the sub-study, participants must be enrolled in the PROSPER trial. We plan to enroll 100 participants from the parent trial in this pilot study, 50 participants from each arm of the parent trial. The inclusion and exclusion criteria for the sub-study are the same as the parent trial.
- b. *Inclusion criteria:* Adult patients (> 18 years of age), English-speaking and able to complete consent and survey materials are eligible to participate. Potential participants must be admitted to the hospital for an anticipated minimum of 3 nights.
- c. *Exclusion criteria:* Vulnerable populations (pregnant, incarcerated, history of delirium, suicidal ideation, ischemic stroke with measurable neurologic deficit, cerebral palsy, seizures), primary brain tumor/metastases patients) are not eligible. Patients concurrently enrolled in contact isolation with SARS-CoV2 will be excluded. Lastly, hospice or hospice-bound patients will also be excluded. Any patient can remove themselves from the study at any point.

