#### 4.4 Study Methods

- a. Study design: The pilot sub-study will be integrated into the parent trial. This pilot study leverages a twogroup, pre-post test design to conduct preliminary tests for differences between the experimental arm (PROSPER intervention with digital vital sign monitoring) and the control arm (PROSPER intervention without digital vital sign monitoring) on objective sleep parameters and patient reported sleep disturbances and fatigue.
- b. Recruitment: Once participants are enrolled in the parent trial, they will be evaluated for inclusion in the pilot sub-study based on the availability of the device that measures objective sleep parameters (Actiwatch Spectrum Pro®). Thirty wrist actigraphy devices (Actiwatch Spectrum Pro®) are available for use at any given time. Fifty participants from the patient care units designated as the intervention arm for the parent trial will be enrolled as treatment patients in the substudy; fifty participants from the patient care units designated as the control arm will be enrolled as control patients in the substudy. Participants will be consecutively enrolled in the sub-study as they are enrolled in the parent study although enrollment may pause if wrist actigraphy devices are not available.
- c. Instrumentation: Objective sleep parameters will be assessed with the Actiwatch Spectrum Pro® during the course of hospitalization, consistent with the parent trial. Patient-reported sleep disturbances will be measured with the PROMIS Sleep Disturbance Adult Short Form. Patient-reported fatigue will be measured in real-time with a one-time global fatigue intensity rating over the course of the hospitalization and the PROMIS Fatigue Adult Short Form. The PROMIS instruments will be completed upon enrollment and discharge +/- 1 day, consistent with the parent trial.

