- e. *Fatigue:* Fatigue will be measured with a one-item fatigue intensity scale, using computerized ecological momentary assessment (real-time assessment) and the Fatigue Adult Short Form (PROMIS instrument). The Actiwatch Spectrum Pro® (Phillips Respironics, Bend, OR) contains a subjective event marker on the face of the activity monitor. This subjective event marker will be used as a real-time, single-item, global, self-report scale to measure real-time fatigue intensity. The fatigue intensity scores range from 0 (no fatigue) to 10 (worst). This rating of fatigue is particularly attractive for use in fatigued people due to ease of use and ability to capture repeated real-time measurements of fatigue throughout the day. While numeric intensity ratings do not provide information regarding the multidimensional nature of fatigue, this type of scale is suggested for use as a fatigue-screening device in clinical situations. A computerized ecological momentary assessment approach to collecting the real-time fatigue data was chosen to allow for improved documentation of compliance, avoid the problems with recall inaccuracies, and improve compliance. Data entered into the subjective event marker are stored in the onboard memory of the wrist actigraphy device.

We successfully used this computerized methodology with people with cancer, such as hematopoietic cell transplantation patients. Fatigue will also be measured using the PROMIS Fatigue Adult Short Form. The Adult Short Forms of the PROMIS instruments, including fatigue, are described together and in detail below.

f. Sleep Disturbance and Fatigue PROMIS Instruments: In concert with the NIH's move to utilize common data elements for research related to symptom science, PROMIS instruments will be used to assess patient-reported symptoms. We will use the Adult Short Forms for fatigue and sleep disturbances. These instruments are reliable, valid, and precise. Computerized versions will be used. The PROMIS instruments use a 5-point Likert scale and employ 7-day recall. Higher scores indicate higher levels of fatigue and sleep disturbances. Scores on all instruments are standardized (M = 50, SD = 10) and normed to a reference (U.S.) population; thus, enabling normative comparisons and providing an interpretative context for scores.

Table.	Variables	and	Measurement

Variable	Measure		

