#### **Richards-Campbell Sleep Questionnaire**

You are now ready to begin to answer the questions. Place your "X" anywhere on the answer line that you feel best describes your sleep last night.

1. 1	dy sleep last night was:	
	Deep Sleep	Light Sleep

2. Last night, the first time I got to sleep, I:

Fell	Just Never
Asleep	Could Fall
Almost	Asleep
Immediately	

3. Last night I was:

Awake	
Very	Awake All
Little	Night Long

4. Last night, when I woke up or was awakened, I:

Got Back	Couldn't
To Sleep	Get Back To
Immediately	Sleep

5. I would describe my sleep last night as:

A Good	A Bad
Night's	Night's
Sleep	Sleep

nsidered

2022-0190 v.23Mar2023 Page 14 of 18

Hospital Anxiety and Depression Scale (HADS) Instructions: Doctors are aware that emotions play an important part in most illnesses. If your doctor knows about these feelings he or she will be able to help you more. This questionnaire is designed to help your doctor know how you feel. Read each item and circle the reply which comes closest to how you have been feeling in the past week. Don't take too long over your replies: your immediate reaction to each item will probably be more accurate than a long thought out response.

I feel tense or 'wound up':	A	I feel as if I am slowed down:	D
Most of the time	3	Nearly all of the time	3
A lot of the time	2	Very often	2
Time to time, occasionally	1	Sometimes	1
Not at all	0	Not at all	0
I still enjoy the things I used to enjoy:	D	I get a sort of frightened feeling like 'butterflies in the stomach':	A
Definitely as much	0	Not at all	0
Not quite so much	1	Occasionally	1
Only a little	2	Quite often	2
Not at all	3	Very often	3
get a sort of frightened feeling like something awful is about to happen:	A	I have lost interest in my appearance:	D
Very definitely and guite badly	3	Definitely	3
res, but not too badly	2	I don't take as much care as I should	2
A little, but it doesn't worry me	1	I may not take guite as much care	1
Not at all	0	I take just as much care as ever	0
can laugh and see the funny side of things:	D	I feel restless as if I have to be on the	A
As much as I always could	0	Very much indeed	3
Not quite so much now	1	Quite a lot	2
Definitely not so much now	2	Not very much	1
Not at all	3	Not at all	0
Worrying thoughts go through my mind:	Α	I look forward with enjoyment to things:	D
A great deal of the time	3	A much as I ever did	0
A lot of the time	2	Rather less than I used to	1
From time to time but not too often	1	Definitely less than I used to	3

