#### Fatigue – Short Form 8a

#### Please respond to each question or statement by marking one box per row.

	During the past 7 days	Not at all	A little bit	Somewhat	Quite a bit	Very much
HI7	I feel fatigued		2	3	4	5
AN3	I have trouble starting things because I am tired	$\square$		□ 3	$\square$ 4	5
	In the past 7 days					
FATEXP41	How run-down did you feel on average?		2	3	$\square$ 4	5
FATEXP40	How fatigued were you on average?		2 2	3	$\square$	5
FATEXP35	How much were you bothered by your fatigue on average?		2 2	3	$\square$ 4	□ 5
FATIMP49	To what degree did your fatigue interfere with your physical functioning?			□ 3	$\square$ 4	5
	In the past 7 days	Never	Rarely	Sometimes	Often	Always
FATIMP3	How often did you have to push yourself to get things done because of your fatigue?		2 2	3	4	□ 5
FATIMP16	How often did you have trouble finishing things because of your fatigue?					5

PROMIS® Item Bank v1.0 - Sleep Disturbance - Short Form 8a

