### Sleep Disturbance – Short Form 8a

#### Please respond to each question or statement by marking one box per row.

		Very poor	Poor	Fair	Good	Very good
Sleep109	My sleep quality was	5	4	3	2	1
	In the past 7 days	Not at all	A little bit	Somewhat	Quite a bit	Very much
Sleep116	My sleep was refreshing	5	4	3	2	1
Sleep20	I had a problem with my sleep		2	3	$\square$	5
Sleep44	I had difficulty falling asleep			3	$\square$	5
Sleep108	My sleep was restless			3	$\square$	5
Sleep72	I tried hard to get to sleep		2	3	4	5
Sleep67	I worried about not being able to fall asleep		2 2	3	4	5
Sleep115	I was satisfied with my sleep	5	4	3	2	

#### In the past 7 days...

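### For 3-4 night stays, the 7-day recall of the discharge PROMIS forms and HADS covers mostly nights before the intervention, which pulls the between-arm contrast on these secondary outcomes toward zero

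*Combined protocol and SAP*

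**What the plan says.** Section 4.4 Study Methods, item f, gives the recall period: "The PROMIS instruments use a 5-point Likert scale and employ 7-day recall". The forms in the Appendix agree: the Fatigue short form is headed "During the past 7 days" and the Sleep Disturbance short form "In the past 7 days". Item c of the same section gives the timing: "The PROMIS instruments will be completed upon enrollment and discharge +/- 1 day, consistent with the parent trial". The HADS printed in the Appendix tells patients to "circle the reply which comes closest to how you have been feeling in the past week", and Table 2 (section 3.9) schedules it at admission and at discharge, plus or minus a day.

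On exposure, section 4.3 states: "Potential participants must be admitted to the hospital for an anticipated minimum of 3 nights". Section 3.2 sets the same 3-night minimum for the parent trial. Section 3.5 adds: "Research coordinators will approach patients to participate in the study within 1-2 days of admission". Sub-study enrolment follows parent enrolment (4.4 Study Methods, item b).

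Section 4.5b analyses PROMIS and real-time fatigue with independent-samples t-tests, described as comparing the arms over the hospital stay. The ANCOVA with baseline and length of stay is in 4.5a, for the objective sleep parameters. Nothing in the plan shortens the recall, requires a minimum number of on-study nights before the discharge form, or adjusts PROMIS for baseline or stay.

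**The concern.** The sub-study's secondary objective (4.2b) is the effect of replacing night-time vital-sign checks with the device on fatigue and sleep disturbance. Objective 1.2c asks the same of mood in the parent trial. A form that looks back 7 days can show that effect only through the nights the patient spent on study. When the stay is short and enrolment is a day or two in, most of the recalled period is the time at home and the first hospital nights, when the arms did not yet differ by device.

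The difference between arms then shrinks even if the intervention works on the nights it is used. The sub-study exists to supply preliminary effect estimates, so a diluted estimate could misinform a later trial. A null PROMIS or HADS result would also be hard to interpret.

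**Working it through.** The documents give no power or precision figure for PROMIS or HADS, so there is no stated figure to reproduce. The check is a count of nights.

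**Inputs.** Recall window: 7 nights before the form (4.4 Study Methods, item f; Appendix). Stay *L*: at least 3 nights (3.2, 4.3). Enrolment *d* nights after admission: 1 or 2 (3.5), with 0 as the best case. Form completed on the day of discharge, or one day either side. Device use is assumed to begin at enrolment; no start time is stated, but section 3.7 places device teaching in the coordinators' on-boarding.

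**Formula.** With the form completed on the day of discharge, on-study nights in the window = min(7, *L* − *d*).

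| Stay *L* | *d* = 0 | *d* = 1 | *d* = 2 |
|---|---|---|---|
| 3 | 3 of 7 | 2 of 7 | 1 of 7 |
| 4 | 4 of 7 | 3 of 7 | 2 of 7 |
| 5 | 5 of 7 | 4 of 7 | 3 of 7 |
| 6 | 6 of 7 | 5 of 7 | 4 of 7 |
| 8 | 7 of 7 | 7 of 7 | 6 of 7 |
| 9 | 7 of 7 | 7 of 7 | 7 of 7 |

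At 3 nights with *d* = 1-2, the exposed share is 1/7 to 2/7 = 14% to 29%. A form completed one day early loses another night: with *L* = 3 and *d* = 2, none of the 7 nights is on study. A form completed one day late replaces one recalled night with a night at home.

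**Illustration of the cost.** Assume the score moves in proportion to the share of exposed nights, and take a hypothetical true effect of 5 T-score points:

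- 3 nights: 5 × 1/7 = 0.7 to 5 × 2/7 = 1.4 points.
- 5 nights: 5 × 3/7 = 2.1 to 5 × 4/7 = 2.9 points.

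With 50 per arm (4.3) and the reference-population SD of 10 (4.4 Study Methods, item f), the 95% confidence-interval half-width is 1.984 × 10 × √(2/50) = 3.97 points.

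At two-sided alpha 0.05 (assumed), the difference detectable with 80% power is (1.960 + 0.842) × 10 × √(2/50) = 5.6 points. If every participant had a 3-night stay, that effect diluted to 2/7 or 1/7 would have power of about 12% or 6% in its own direction. Restoring 80% would take 50 × (7/2)² ≈ 613 or 50 × 7² = 2,450 per arm. These are bounds for the shortest stay, not forecasts for the trial.

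**The case against.** Three nights is the minimum stay, not a typical one. With enrolment on day 1, on-study nights are already the majority at 5 nights, and section 3.5 allows enrolment sooner than day 1. Without a length-of-stay distribution, the share of patients affected cannot be computed. This stands, and it limits the point to short stays. The proportional-dilution figures are also only illustrative: if patients weigh recent nights more heavily, the loss is smaller.

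Part of the problem is already covered. Item e of 4.4 Study Methods chose the real-time rating partly to avoid recall error, and 4.2b names it first. The sub-study's primary outcome is actigraphy. Fatigue and sleep therefore each have a measure without this fault. That stands too, but 4.2b and 4.5b set no order among the measures, and mood has no alternative to HADS.

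A reader might infer that overlap between the enrolment and discharge windows (5-6 of 7 days at a 3-night stay) biases the comparison. It does not. The planned test is between arms, and the overlap is the same loss of exposed nights seen from the other side. In a baseline-adjusted model, the resulting correlation would help precision.

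A reader might also infer that dilution is worse in the intervention arm because the trial expects the device to shorten stay. That rests on an unproven hypothesis. Controls have no device nights, so what is diluted is the contrast between arms. Nor does any text plan to read a null as absence of effect.

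**Conclusion.** The point holds for stays of 3-4 nights with enrolment 1-2 days after admission and the form completed at discharge: 1-3 of the 7 recalled nights are then on study. It does not support the broader inference that discharge PROMIS and HADS scores mostly describe pre-intervention days for participants in general. The expected direction is toward zero; the overall size is unknown. The conclusion assumes that device use starts at enrolment and that the form reflects the week it asks about.

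The outcomes concerned are secondary: PROMIS in a pilot sub-study and HADS in the parent trial. If HADS is completed strictly at admission its baseline is free of study nights, but its discharge window has the same shortfall. Actigraphy, real-time fatigue and the last-night sleep form are not affected by the 7-day recall. The EQ-5D-5L form is not printed in the Appendix, so nothing is concluded about the parent trial's primary outcome.

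**What to change.** Before results are seen, change 4.2b and 4.5b as follows, with a matching statement for HADS in 3.9 or 3.10:

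- Name the real-time 0-10 fatigue rating as the lead fatigue outcome. First reconcile 4.4 Study Methods, item c, which calls it a one-time rating, with 4.4 Data Collection, which asks for it five times a day.
- Name an in-hospital Richards-Campbell score as the lead patient-reported sleep outcome, once Table 2 is reconciled: it labels the form daily but schedules it at admission and discharge only. Specify in-hospital nights, because a form completed the day after discharge could describe a night at home.
- Replace the plain t-test for discharge PROMIS with ANCOVA on the enrolment score. This can improve precision; it does not undo the dilution.
- Add a sensitivity analysis by number of on-study nights, labelled descriptive because stay may itself be affected by the intervention.
- Label discharge PROMIS and HADS as supportive, and state that a null on them is not evidence of no effect.

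Keep the standard 7-day stem at both time points. Rewording it at discharge only would give up the normed scores and make the two forms ask about different periods.

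The cost is protocol wording, a little more analysis work and less weight on PROMIS. The fatigue step needs no new data if the five-daily schedule is the intended one. Whether the sleep step does depends on how Table 2 is reconciled.

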#### 4.4 Data Collection

Upon enrollment to the pilot sub-study, the wrist actigraph will be placed on the non-dominant wrist. The research staff will review real-time fatigue intensity rating procedures and instruct participants to leave the device in place for the duration of the hospitalization. Participants will be directed to carry on with normal activities. They will be asked to rate the intensity of fatigue at that moment in time on a 0 (no fatigue) to 10 (worst fatigue) scale five times during each day (upon awakening, 10:00 am, 2:00 pm, 6:00 pm, and at bedtime). An audible and vibratory alarm on the wrist actigraph will sound at preset times (10:00 am, 2:00 pm, and 6:00 pm) to remind participants to complete the real-time fatigue assessment. They will enter the rating directly into the subjective event marker of the wrist actigraph. Because of the expected time variability associated with awakening and going to bed, it will not be possible to program the Actiwatch Spectrum Pro® to alarm at these times. Participants will complete the PROMIS Sleep Disturbance and Fatigue questionnaires upon enrollment and hospital discharge +/- 1 day, in keeping with the parent trial data collection periods.

#### 4.5 Statistical Analysis

Prior to analysis of the specific aims, we will clean the data, check internal consistency of scales using Crombach's alpha coefficient, and check distributions using both descriptive statistics and graphical displays.

2022-0190 v.23Mar2023 Page 9 of 18

#### a. Primary Objective

For each variable, differences between PROSPER with digital vital sign monitoring (the experimental group) and PROSPER without digital vital sign monitoring (the control group) will be calculated and reported with 95% twosided confidence intervals. Further exploratory analysis with ANCOVA models will incorporate covariates of baseline measures and length of stay to assess the relative efficiency gain of each covariate, as well as potential for confounding.

Based on previous work by the investigators, the confidence interval for the difference between groups should have expected lengths of no more than 54 (total sleep time, min), 12 (sleep latency, min), 5 (sleep efficiency, %), 17 (frequency and duration of awakenings after sleep onset, min), and 5 (number of awakenings).

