#### 3.10 Statistical Analysis Plan

Means with standard deviations, frequencies and percentages will be used to convey descriptive statistics. Standard tests of association (chi-squared, t-tests) will be used for comparing characteristics between the control and intervention arm. Inverse probability weighting using propensity scores modeled from baseline covariates and instrumental variable analysis will be the quasi-experimental approach used to minimize any confounding bias from our pseudorandomization process. We will model most outcomes with weighted multivariate generalized mixed effects regression models, focusing primarily on estimate the average treatment effect. The effect of unit will be modeled using a random intercept term. Care utilization outcomes will be compared using standard time-to-event models and log-rank testing. Final analyses will be performed when all data has been entered, cleaned, and locked.

All analyses will be based on an intent-to-treat framework. For missing covariate values, a multiple imputation approach will be used. Outcomes will be assumed to be missing at random; a sensitivity analysis will be conducted to assess the robustness of significant findings to different magnitudes of missing data mechanisms.

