#### 3.11 Sample size justification

Preliminary calculations, based on an estimated conservative change of 10% from baselines scores in QOL, as measured by the EQ-5D instrument total score (with a baseline of mean of 13 units and standard deviation of 5 units). We expect to detect a significant change with at least 80% power using 250 patients per treatment arm. To account for increased estimation variance due to propensity score-based reweighting (and a small rate of drop-out after enrollment), we plan to enroll 350 patients per treatment arm to ensure a reasonable expectation of significance.

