#### b. Secondary Objective

Descriptive data will be computed for the real-time fatigue scores, PROMIS Fatigue, and PROMIS Sleep disturbance. Preliminary analysis will be conducted using a two-sided independent samples *t*-tests comparing PROSPER with digital vital sign monitoring (experimental group) compared to PROSPER without digital vital sign monitoring (control group) over the course of the hospitalization.

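### The sub-study's main comparisons are crude, although the parent plan weights for the same bed-based allocation, so its preliminary effects are open to possible confounding

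*Combined protocol and SAP*

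**What the plan says.** **Parent trial.** Section 3.4 places patients in an arm by the unit where a bed is free: one of two sides of P10 for colorectal surgery, and G21 or G22 for hospitalist medicine. Section 3.7 adds that clinical factors, such as the need for isolation and nursing availability, also influence the room. Section 3.10 responds to this: "Inverse probability weighting using propensity scores modeled from baseline covariates and instrumental variable analysis will be the quasi-experimental approach", and the stated aim is "to minimize any confounding bias from our pseudorandomization process". It also models unit as a random intercept. Section 3.11 raises enrolment from 250 to 350 per arm, partly "To account for increased estimation variance due to propensity score-based reweighting" and partly for drop-out.

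**Sub-study.** Sections 4.3 and 4.4 take 50 participants from the parent's intervention units and 50 from its control units, consecutively as actigraphs are available. Section 4.5a reports arm differences that "will be calculated and reported with 95% twosided confidence intervals". It continues: "Further exploratory analysis with ANCOVA models will incorporate covariates of baseline measures and length of stay", and the purpose is "to assess the relative efficiency gain of each covariate, as well as potential for confounding". Section 4.5b states: "Preliminary analysis will be conducted using a two-sided independent samples" t-tests, with no adjusted analysis. Nothing in section 4.5 refers back to section 3.10.

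**The concern.** Both analyses rest on one allocation mechanism. If that mechanism justifies weighting in the parent trial, the same patients' actigraphy and PROMIS comparisons need comparable protection, or a reason why they do not. The plan gives no such reason.

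Section 4.2 sets out to determine preliminary effects of the intervention with digital monitoring, which is a comparative aim. Someone planning a later trial would read the crude difference as an estimate of what the device does. If case mix differs systematically between the units, part of that difference belongs to the patients and not to the device. The confidence interval does not cover that part, because it reflects sampling error only.

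**Working it through.** **1. Does any planned sub-study analysis do the job of the parent's weighting?**

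| Feature | Parent (3.10) | Sub-study primary (4.5a) | Sub-study secondary (4.5b) |
|---|---|---|---|
| Main estimate | Weighted mixed model | Crude difference | t-test |
| Propensity weighting | Yes | No | No |
| Unit term | Random intercept | None | None |
| Covariate adjustment | Yes | Exploratory ANCOVA only | None |

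The ANCOVA names confounding as one of its purposes, but it falls short in four ways.
- It is labelled exploratory, so it is not the estimate reported for the objective.
- It does not extend to real-time fatigue, PROMIS Fatigue or PROMIS Sleep Disturbance.
- It does not name service. Two services feed each arm, and the quota of 50 per arm is not stratified by service.
- One of its two covariates is length of stay. This is known only after allocation, and the parent Hypothesis section expects the intervention to shorten it. Adjusting for it can remove part of the effect or introduce bias.

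**2. What the stated interval lengths imply.** Section 4.5a gives expected lengths of at most 54 min (total sleep time), 12 min (latency), 5% (efficiency), 17 min (awakenings after onset) and 5 (number of awakenings). It gives no SD, so the lengths cannot be reproduced, only inverted. Assume an unadjusted t interval with 50 evaluable per arm:

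length = 2 × t(0.975, 98) × SD × √(2/50)

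The implied SDs are 68.0, 15.1, 6.3, 21.4 and 6.3. For total sleep time, SE = 68.0 × √(2/50) = 68.0 × 0.2 = 13.6 min.

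**3. Scale of a possible bias (assumed values).** For bias b, coverage = Φ(1.96 − b/SE) − Φ(−1.96 − b/SE). Since SE = 0.2 SD, the ratio b/SE is b (in SDs) divided by 0.2.

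| Assumed bias | Total sleep time | b/SE | Coverage of nominal 95% interval |
|---|---|---|---|
| 0.1 SD | 6.8 min | 0.5 | 92% |
| 0.2 SD | 13.6 min | 1.0 | 83% |
| 0.3 SD | 20.4 min | 1.5 | 68% |

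No figure in the documents says which row applies, or whether any does.

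**4. What weighting would do to precision.** Parent check first: 10% of 13 is 1.3 units. With SD 5 and two-sided alpha 0.05 (assumed), 80% power needs 233 per arm, and 250 gives 82.8%, in line with section 3.11. The step to 350 is a factor of 350/250 = 1.4. It covers weighting and drop-out together, so 1.4 is an upper value for weighting alone. On the assumptions of step 2, new length = stated length × √(inflation):

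| Variance inflation | Total-sleep-time length | Per arm to keep 54 min |
|---|---|---|
| 1.1 | 54 × √1.1 = 56.6 min | 55 |
| 1.2 | 54 × √1.2 = 59.2 min | 60 |
| 1.4 | 54 × √1.4 = 63.9 min | 70 |

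At 1.4 the other four lengths become 14.2 min, 5.9%, 20.1 min and 5.9.

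**The case against.** The sub-study is a pilot with hypotheses about trends. Crude differences with intervals, followed by an exploratory adjusted model, are a common and defensible pilot analysis. Sections 3.4 and 3.7 describe bed assignment as driven by availability and independent of patient or team preference. Each service contributes one intervention and one control unit, so service mix need not differ between arms. Section 3.10 weights against any confounding and does not assert that confounding exists. All of this stands. It lowers the weight of the point, but it does not explain why the same allocation is handled differently within one document.

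Three stronger readings are tempting, and the documents support none of them.
- **The sub-study estimates are confounded.** Only exposure to possible confounding can be shown. Nothing gives its size or direction, and no mechanism by which device availability would select differently by arm is described.
- **Arms of 50 add confounding through chance imbalance.** Chance imbalance is random error, and the interval already allows for it.
- **The stated interval lengths omit weighting and loss.** They are given as upper bounds drawn from earlier work, without an SD, an evaluable number or a formula. Inverting them on the assumption of no allowance cannot then prove that none was made.

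**Conclusion.** The inconsistency is real, modest and cheap to remove. The main sub-study comparisons lack the protection that the parent plan considers prudent for the same allocation. The exploratory ANCOVA does not supply it, and section 4.5b has no adjustment at all. The conclusion about method rests on the text alone.

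The numbers are conditional. The coverage figures of 92%, 83% and 68% follow from assumed biases of 0.1, 0.2 and 0.3 SD. The range of about 57 to 64 min for the total-sleep-time interval assumes that 54 min was derived unweighted with 50 evaluable per arm, and that the inflation lies between 1.1 and 1.4.

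**What to change.** - In 4.5a and 4.5b, make the main estimate the arm difference adjusted for pre-allocation covariates, including service. Use either the parent's propensity weights, with balance (service included) checked in the 100 sub-study participants, or direct covariate adjustment. Scores fitted on the whole parent sample do not guarantee balance in this subset.
- Report the crude difference beside it.
- Do not use length of stay as a confounder adjustment.
- State the expected interval lengths for the estimator actually used, with the SDs, the evaluable number per arm and any variance inflation assumed.

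**Cost.** The analysis wording changes; no extra patients, visits or data collection are needed. Intervals may be somewhat wider if weighting is used. The weighted version must also wait for the parent scores, since section 3.10 places final analyses after data lock; covariate adjustment avoids that wait. Neither option removes differences between the units themselves, because arm and unit coincide within each service. That limit should be stated with the results.
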